3.5.2 Precautions to be applied for dosing of different treatment groups

All treatment groups will enrol in parallel. A human study has already been completed at significantly higher dose levels with no safety concerns identified. Should a safety concern arise an *ad hoc* SRC will be arranged. In addition, study AR/stopping rules are in place for the duration of the study.

The anticipated exposure after the highest dose of [REDACTED] mg is expected to be [REDACTED] times less than the correspondent NOAEL exposure in animals and humans.

3.5.3 Monitoring and communication of adverse events/reactions

AEs will be continuously monitored throughout the study from the signing of the ICF until the last follow-up assessment. Each AE reported will be assessed by a trained Research Physician (RP) who will ensure that the event is dealt with appropriately, based on clinical findings, study protocol, study operations manual and Richmond Pharmacology Limited (RPL) Standard Operating Procedures (SOPs). AEs will be documented in the participants' source Case Report Forms (CRFs).

The collection, evaluation and reporting of adverse events/reactions arising from this clinical study will be performed in accordance with:

- "Detailed guidance on the collection, verification and presentation of adverse event/reaction reports arising from clinical trials on medicinal products for human use ('CT-3') (2011/C 172/01)".
- International Council for Harmonization (ICH) guideline E2F "Note for guidance on development safety update reports (DSUR)".
- International Council for Harmonization (ICH) guideline E2A "Clinical Safety Data Management: Definitions and Standards for Expedited Reporting".

If any information relating to the IMP in this study becomes available after the submission of a final protocol to the Competent Authority which may impact on the conduct of the study, including but not limited to the risk and benefit evaluations underpinning approvals and participant's consent, Upstream Bio shall notify RPL in writing as soon as practically possible and the parties will agree, in writing, what steps need to be taken if any.

3.5.4 Investigator site facilities and personnel

This study will be conducted in a specialized early phase Clinical Pharmacology Unit with on-site resuscitation equipment and medication, in addition to access to an acute hospital with critical care facilities, thus ensuring direct access to equipment and staff for resuscitating and stabilizing participants in acute medical conditions and emergencies. The study is conducted by an experienced PI and well-trained medical and technical staff with ample experience in the conduct of early phase clinical studies.

The study is designed to closely monitor, treat and communicate potential expected adverse reactions as well as potential unexpected adverse events.

4. DECISION-MAKING, RULES AND LIMITS

4.1 Rules and limits governing decision-making

The criteria and rules that will govern Investigator decisions are:

1. AE stopping rules (Table 9 and Table 10)
2. Adaptive features and their limits (Table 6).

4.2 Safety Review Committee

There are no SRC meetings scheduled during the study. Results of the SAD study performed with UPB-101 or placebo were reported in Section 1. In that clinical study, UPB-101 was safe and well-tolerated. The highest dose administered was [REDACTED] mg/kg (the equivalent of approximately [REDACTED] mg), while the highest proposed dose of UPB-101 in this study is more than [REDACTED] lower ([REDACTED] mg). The predicted exposure levels for the highest planned dose in this study are [REDACTED] than those that were safe and well tolerated in the SAD study.

However, if required due to Investigator or Sponsor safety concerns or reaching of a dose-limiting AR stopping rule necessitating an *ad hoc* SRC, it will consist of, as a minimum:

- RPL Principal Investigator or delegate
- Upstream Bio Medical Monitor or delegate

Further internal or external experts such as a pharmacokineticist, and/or a statistician, may be consulted by the SRC as necessary. Any additional information, if required will be included in the SOM.

They will review the required data in accordance with Table 8, Table 9, and Table 10. The safety data to be reviewed will include listings of TEAEs, clinically significant vital signs, physical examinations, ECGs, clinical laboratory results, and available PK data, as well as participant disposition.

4.3 Adverse reaction (AR) rules

An AR is any AE where there is a reasonable possibility of it being related to the IMP(s). ARs will be classified in accordance with Sections 8.1 and 8.3 to support standardized recording and reporting.

- Seriousness will be assessed using the criteria in Section 8.1.
- Severity and causality will be assessed using the criteria in Section 8.3.

Seriousness and severity are assessed independently. 'Severity' characterizes the intensity of an AE. 'Serious' is a regulatory definition and serves to define and trigger regulatory reporting obligations.

Seriousness and severity grade both have consequences when applying AR rules. Seriousness of an AR always overrides the severity grade and the rules for Serious AR should be applied, irrespective of severity grade.

These rules will only apply to treatment-emergent AEs/SAEs where there is a reasonable possibility of relationship to the IMP (i.e., ARs and SARs). Every AE will be assessed in the following order:

- 1) the impact on the individual participant

- 2) the impact on the treatment group (and higher dose treatment groups)
- 3) the impact on continuation or suspension of the overall study.

Dose-limiting ARs are specific ARs that for the purposes of this study, depending on their severity grading, the frequency at which they occur and their 'seriousness', will result in either:

- 1) Suspension of dosing at the same or higher dose or
- 2) Suspension of dosing of all dose/treatment groups (i.e., whole study suspension).

This is a single-dose study and therefore individual AR rules are not applicable. However, if a participant displays immediate signs of an AR whilst UPB-101 is being administered, study drug administration will be immediately abandoned, and the participant will be reviewed and managed in line with current clinical guidelines.

Table 8 shows the definition of the dose-limiting ARs for this study.

Table 8: Dose-limiting adverse reactions

Severe	Serious
Haematological Adverse Reaction Grading	

• Hb drop of >25% from baseline on Day -1 (only for values below the laboratory reference range).• Platelet count drop of >25% from baseline on Day-1 (only for values outside the laboratory reference range), or absolute value of <80 x10⁹/L.• Clinically significant neutrophil drop^a• Any other haematological toxicity which in the opinion of the Investigator would preclude further dosing of participants at this dose level or higher	
Liver Adverse Reaction Grading	

• ALT or AST value >3 x and <5 x ULN• ALT or AST value >3 x and <5 x ULN and symptomatic^b OR ALT or AST value >5x ULN +/- symptoms^b	
• Potential drug-induced liver injury (DILI), as defined by ALT or AST value >3 x ULN together with bilirubin >2 x ULN.
Cardiac Adverse Reaction Grading	

• QT interval prolongation: A prolongation of the uncorrected QT interval of greater than 500 ms, using consistent, technically valid triplicate ECG.	
Injection Site Reaction Grading	

• Ulceration or necrosis• Severe tissue damage• Operative intervention indicated	

Severe	Serious
Other Adverse Reaction Grading (Global Clinical Assessment)	

Overall clinical condition is asymptomatic or is symptomatic with one or more of the following characteristics:
 
 • Significant impact on usual self-care activities • Inability to perform usual social and functional activities • The deviation from reference range for the population and from the participant's baseline has significant clinical impact, it is acute safety concern or unanticipated risk and requires close and continuous monitoring • The reversibility of the condition to baseline condition takes significantly longer than desirable or anticipated, with significant impact on the participant's wellbeing • Intervention or treatment essential to treat the acute manifestations and to prevent worsening. 	
 • Any AR that meets seriousness criteria (i.e., an SAE).

ALT=alanine aminotransferase; AST=aspartate aminotransferase; ECG=electrocardiogram; Hb=haemoglobin; ULN=upper limit of normal

^a Clinically significant being defined as requiring of additional investigation or treatment to manage the finding.

^b Symptoms or signs include fatigue, nausea, vomiting, right upper quadrant pain or tenderness, fever, rash and/or eosinophilia (eosinophil percent or count above the ULN).

The treatment group and study Stopping Rules for dose-limiting ARs are described in Table 9 and Table 10 respectively.

Table 9: Treatment group stopping rules

Action	Frequency of dose-limiting ARs	
	Severe	Serious
Dosing of remainder of treatment group (and all other treatment groups of the same or higher dose) to be suspended ^a while dosing of lower dose treatment groups may continue	≥ 2	≥ 1 deemed at least possibly related to the study drug

^a Continuation of dosing requires regulatory approval via a substantial amendment.

Table 10: Study stopping rules

Action	Frequency of dose-limiting ARs	
	Severe	Serious
All dosing suspended ^a		≥1 where SAE deemed at least possibly related to the study drug and is either life threatening or leads to death

^a Continuation of dosing requires regulatory approval via a substantial amendment.

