3.5 Rationale for study design and dose of UPB-101

This study is designed for the purpose to increase understanding of the clinical profile of UPB-101.

The rationale for investigating a possible difference in the PK of UPB-101 attributable to the Japanese ethnicity is to determine the optimal dose and dosing frequency of UPB-101 in this specific population, which due to genetic differences may be different to that of other ethnicities. 24 Japanese participants (8 participants across 3 treatment groups) and 8 NJNAE participants is sufficient to explore this objective. The NJNEA treatment group will aim to include Caucasian and 2-3 non-Caucasian participants to ensure diversity. They must also be 'non-East-Asian' (i.e., not Chinese, Korean, Mongolian or Taiwanese), as there may be genetic overlap between Japanese and East-Asian participants.

The study will be open label.

Nonclinical and clinical studies have shown no safety concerns for UPB-101 administered in doses significantly higher than the maximum planned dose for this study (█ mg). Therefore, sentinel or ascending dosing is not required. There are also no adaptive features which allow for doses that exceed the maximum planned dose of █ mg, which is well within the safe range of doses already tolerated in the FIH study. As a result, there are no dose escalation rules or dosing decisions to be made between cohorts; therefore, there is no need for an interim SRC review.

All treatment groups will enrol and dose in parallel. On Day 1, Japanese members of the cohort will be randomized to either treatment group 1, 2 or 3, and NJNEA participants will automatically be assigned to treatment group 4. The study will be completed in as few cohorts as operationally possible to minimize period bias. Attempts will be made to include in each cohort at least 2 participants assigned to each of the 4 treatment groups (therefore a minimum of 8 participants per cohort and a maximum of 4 cohorts to complete the study).

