- it is considered medically important (medical and scientific judgement should be exercised in deciding whether other AE/ARs are to be considered serious, such as important medical events that may not be immediately life-threatening or result in death or hospitalization* but may jeopardize the participant or may require intervention to prevent one of the other outcomes listed in the definition above. Examples of such events are intensive treatment in an emergency room or at home for allergic bronchospasm; blood dyscrasias; convulsions that do not result in hospitalization; development of drug dependency or drug abuse).

*'Hospitalization' qualifying for an SAE does not include the following: under 24 hours; admission unrelated to an Adverse Event ,e.g., for labour and delivery, cosmetic surgery, social or administrative for temporary placement (e.g., admission due to lack of transport or support at home); admissions for diagnosis or therapy of a pre-existing condition that has not increased in severity or frequency; protocol-specified admission; pre-planned admission; admission to a rehabilitation or nursing facility; hospice; presentation to emergency departments or other urgent care centres; admissions to hospital in-patient facilities for logistical reasons only that did not result in any therapeutic intervention (e.g., awaiting consultation with and decision by senior medical staff or specialists, or for an investigation that is not immediately available); admissions to hospital in-patient facilities for investigation alone and where no significant abnormality was identified and/or no therapeutic intervention was necessary; same-day out-patient surgery.

An '**Adverse Reaction (AR)**' is a response to a medicinal product that is noxious and unintended, which occurs at any dose (in pre-approval clinical experience) or at doses normally used in man for prophylaxis, diagnosis, or therapy of disease or for modification of physiological function (in post-approval clinical experience). The term 'reaction' means that a causal relationship between a medicinal product and an Adverse Event is at least a reasonable possibility. This means that there are facts (evidence) or arguments to suggest a causal relationship.

A '**Serious Adverse Reaction (SAR)**' is any AR that fulfils the criteria of seriousness, as defined above.

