Possibly: A reaction that follows a reasonable temporal sequence from administration of study drug; that follows a known or expected response pattern to the study drug, but that could reasonably have been produced by a number of other factors including underlying disease, complications, concomitant drugs, or concurrent treatments.

Not Related: A reaction for which sufficient data exist to indicate that the aetiology is unrelated to the study drug.

The Investigator should also comment on the source document whether an AE is not related to the study treatment but is related to study participation (e.g., study procedures).

The relationship to the study medication will be classified according to the categories described in Table 16.

8.3.3 Practical application of severity grading and causality assessment in relation to AR rules

Step 1: Confirm diagnosis of the AE/AR (exact term will be decided using the MedDRA), once the root cause of the clinical manifestations has been determined (rather than diagnosing individual signs, symptoms, assessments, and measurements).

Step 2: Distinguish between serious and non-serious AE/ARs using the standard definitions of what constitutes a 'serious' AE/AR (see Section 8.2).

Step 3: Assess whether there is a reasonable possibility of a relationship with the IMP.

Step 4: If there is a reasonable possibility that it is related to the IMP, apply the correct AR rules

- **'serious AR':** The classification as 'serious' (see Sections 8.2 and 8.3) overrides the application of the categorical (mild/moderate/severe) grading system. The rules for serious AR must be applied. Categorical grading (moderate or severe) should also be independently recorded to add additional information.
- **'non-serious AR':**
 - some individual clinical manifestations, signs, symptoms, assessments, or measurements (such as QT prolongation, anaemia, thrombocytopenia, liver enzyme abnormalities) have pre-defined special AR rules, which should be applied if they occur
 - for all other non-serious ARs use the global clinical assessment and categorical grading method outlined above to assign the severity grade (Table 16). Consider:
 - the clinical significance (including presence or absence of clinical symptoms)
 - participant populations' specific references ranges and degree of deviations thereof
 - the degree of deviations from baseline
 - timing, duration, and reversibility

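### Table 8's only numeric cardiac stopping criterion is uncorrected QT > 500 ms, so above 60 bpm a related QTcF > 500 ms can miss it and has no numeric route into the stopping count

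*Protocol*

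**What the plan says.** **The stopping rule.** Table 8 in Protocol 4.3 defines the dose-limiting adverse reactions (ARs). Its cardiac part has one entry, in the severe column: "A prolongation of the uncorrected QT interval of greater than 500 ms", on a valid triplicate ECG. It gives no QTcF limit and no change-from-baseline limit, and the serious column is empty for that part. Table 9 suspends a treatment group, and every group at the same or a higher dose, after two severe or one serious dose-limiting AR. Section 4.3 limits the scope: "These rules will only apply to treatment-emergent AEs/SAEs where there is a reasonable possibility of relationship to the IMP".

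**Other routes into the count.** Table 8's global severe row includes a clinically significant deviation from reference range and baseline where "it is acute safety concern or unanticipated risk and requires close and continuous monitoring". The serious column takes "Any AR that meets seriousness criteria". Protocol 8.2 lists the hard serious outcomes (death, immediate threat to life, qualifying hospitalisation, lasting disability) and adds medically important events that "may jeopardize the participant or may require intervention to prevent one of the other outcomes listed in the definition above".

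**How the routes fit together.** Protocol 8.3.3 says that some findings, QT prolongation among them, "have pre-defined special AR rules, which should be applied if they occur". It then says "for all other non-serious ARs use the global clinical assessment and categorical grading method outlined above to assign the severity grade".

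**QT measures elsewhere.** QTcF is the exclusion limit (above 450 ms, Protocol 5.4 criterion 6) and the metric of the categorical analyses, whose top absolute category is above 500 ms (Protocol 10.5, SAP 4.10.6). The site's reference ranges in SAP 4.10.6 give a QTcF limit and none for uncorrected QT. The central laboratory's ranges give 320 to 450 ms for both.

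**The concern.** Uncorrected QT shortens as heart rate rises, so a fixed 500 ms cut-off on it is more lenient at fast rates and stricter at slow ones. A participant could fall in the study's highest QTcF category without meeting the one numeric cardiac criterion for stopping.

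The numeric row carries some weight here. Protocol 3.5 has no sentinel or ascending dosing and no interim safety review, Protocol 4.2 schedules no Safety Review Committee (SRC) meeting, and Protocol 3.5.2 names the stopping rules as a standing precaution. Table 9 works by counting. If one of two related events goes uncounted, the severe count stays at one and the group continues dosing.

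**Working it through.** **Inputs.** Cut-off of 500 ms on uncorrected QT (Table 8). Supine heart rate of 40 to 90 bpm at entry (Protocol 5.4 criterion 7). QTcF entry limit of 450 ms (Protocol 5.4 criterion 6). The plan states no derived figure here to reproduce; 500 ms is a chosen limit.

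**Formula.** The documents name Fridericia's correction without writing it out. I use its standard form: QTcF = QT / RR^(1/3), with RR = 60/HR in seconds. I read the Table 8 row as an absolute QT above 500 ms.

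**Worked case at 80 bpm.** RR = 60/80 = 0.75 s, and 0.75^(1/3) = 0.90856. QT 500 ms gives 500/0.90856 = 550.3 ms. QT 480 ms gives 480/0.90856 = 528.3 ms, which is 528.3 − 450 = 78.3 ms above the entry limit, yet it does not meet the row.

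| HR (bpm) | QTcF when QT = 500 ms | QT when QTcF = 500 ms |
|---|---|---|
| 40 | 436.8 | 572.4 |
| 50 | 470.5 | 531.3 |
| 55 | 485.7 | 514.7 |
| 60 | 500.0 | 500.0 |
| 65 | 513.5 | 486.8 |
| 70 | 526.4 | 475.0 |
| 80 | 550.3 | 454.3 |
| 90 | 572.4 | 436.8 |

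**Above 60 bpm** the missed band runs from just over 500 ms to the middle column: up to 514 ms at 65 bpm, 526 at 70, 550 at 80 and 572 at 90.

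**Below 60 bpm** the row errs on the cautious side. It can be met with QTcF under 500 ms and, below 60 × (450/500)³ = 43.7 bpm, with QTcF under the 450 ms entry limit.

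**Would a missed event be seen?** Yes. QTcF above 500 ms is outside both the site and the central laboratory QTcF ranges. At 65 to 80 bpm the uncorrected QT of a missed event is also above 454 ms, outside the central laboratory's QT range.

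**Would it be counted?** A hard serious outcome counts with no QT figure. Otherwise the event needs the global severe row or a finding that it is medically important. Both are qualitative. Section 8.3.3 leaves the first route open to two readings: QT prolongation belongs to its special rule only, or an ECG that does not meet the special rule passes to the global assessment.

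**The case against.** The case against is substantial.

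- **This is a choice, not an error.** No passage says that stopping should rest on QTcF. Eligibility limits and descriptive tables serve other purposes. This stands: a reader might infer that the protocol contradicts itself or the SAP, and it does not.
- **QTcF is not the only measure in use.** The central laboratory lists an uncorrected QT range, and QT is among the reported ECG parameters. This also stands.
- **The event is covered in substance.** The global row reaches asymptomatic deviations, and its more natural reading takes in an ECG that fails the special rule. A research physician reviews every ECG (Protocol 7.8.2), and any safety concern may suspend enrolment at that dose pending an ad hoc SRC (Protocol 3.5, 4.2). So a reader might infer that a QTcF above 500 ms would go unnoticed or could not stop dosing; the documents do not support that. What remains is that none of these routes sets a QTcF threshold, so two physicians could count the same ECG differently.
- **Judgement is everywhere in Table 8.** Every row needs a relatedness call, and some rows are openly matters of opinion. True, but the cardiac row was given a number, and that number depends on heart rate.
- **The large figures are hypothetical.** They need a QT close to 500 ms at 80 or 90 bpm after at least 10 minutes' supine rest. This is fair. The documents give no post-dose heart rates, so the frequency is unknown.
- **Replacing QT with QTcF would loosen the rule at slow rates.** Correct: the effective QT cut-off would rise from 500 to 531 ms at 50 bpm and 572 ms at 40 bpm. A reader might infer that QTcF should simply take the row over; it should not.

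**Conclusion.** The point holds in limited form. Above 60 bpm a related, treatment-emergent QTcF above 500 ms can miss the only numeric cardiac criterion. Without a hard serious outcome, it then enters the Table 9 count only through routes that have no QTcF threshold.

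The practical impact is small. Each participant receives one dose, so the row protects only those not yet dosed, and Section 3.5 plans "a maximum of 4 cohorts to complete the study". Group suspension needs two severe related events. Table 2 of the Protocol records no cardiovascular effects in human or nonclinical studies.

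The conclusion rests on the standard Fridericia formula, on reading the row as an absolute value, and on taking 40 to 90 bpm, an entry range, as a guide to heart rates on study. It is a gap worth closing because the change is one table row. It is not evidence that anyone was unmonitored or harmed.

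**What to change.** Restate the cardiac row of Table 8 as: *QTcF > 500 ms or uncorrected QT > 500 ms*, with the triplicate-ECG confirmation that the row already requires. Keeping the uncorrected trigger is part of the change, so that no present protection is lost at slow heart rates.

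A criterion of a QTcF increase above 60 ms from baseline is not needed to close this gap. It is already a descriptive category in Protocol 10.5 and SAP 4.10.6, and whether it should also stop dosing is for the medical team, which should confirm the 500 ms threshold too.

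The cost is one table row, by amendment if the protocol is in use. No procedure is added because QTcF is already recorded. The downside is a possible extra suspension, which under Table 9 can be lifted only by a substantial amendment. SAP 4.15 refers to the study as completed; if dosing has ended, the wording can only serve later protocols.
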